8.1 Informed consent procedures

Eligible patients may only be included in the study after providing written (witnessed, where required by law or regulation), IRB/IEC-approved informed consent.

If incapable of doing so, in cases where the patient's representative gives consent, the patient should be informed about the study to the extent possible given his/her understanding. If the patient is capable of doing so, he/she should indicate assent by personally signing and dating the written informed consent document or a separate assent form.

Informed consent must be obtained before conducting any study-specific procedures (i.e. all of the procedures described in the protocol). The process of obtaining informed consent should be documented in the subject source documents.

The date of signing of informed consent (and withdrawal, if later withdrawn) should be documented in the CRF.

Novartis will provide to investigators a proposed informed consent form that complies with the ICH GCP guideline and regulatory requirements and is considered appropriate for this study. Any changes to the proposed consent form suggested by the investigator must be agreed to by Novartis before submission to the IRB/IEC.

Novartis will review the Investigators proposed informed consent form to ensure it complies with the ICH GCP guideline and regulatory requirements and is considered appropriate for this study. Any further changes to the proposed consent form suggested by the investigator must be agreed to by Novartis before submission to the IRB/IEC.

Pregnancy outcomes must be collected for the female partners of any males who took study treatment in this study. Consent to report information regarding these pregnancy outcomes should be obtained from the mother.

Corporate Confidential Information

8.2 Patient demographics/other baseline characteristics

Patient demographic and baseline characteristic data will be collected on all patients at Screening (Visit 1). The following will only be assessed at the Screening Visit and not at subsequent visits:

- Demography
- Medical History/Current medical conditions
- Hepatitis and HIV Screen
- Alcohol Test and Drug Screen

Relevant medical history/current medical conditions data includes data until signature of informed consent. Where possible, diagnoses rather than symptoms will be recorded.

Investigators have the discretion to record abnormal test findings on the medical history CRF whenever in their judgment, the test abnormality occurred prior to the informed consent signature.

8.3 Pharmacodynamics

Pharmacodynamic assessments are specified below. The details for sample collection and assay methods will be specified in the Study Operations Manual (SOM). Samples will be collected and assessments will be performed at the timepoint(s) defined in the [Assessment schedule](#).

In order to better characterize the PD profile, the timing of the sample collection may be altered based on emergent data. The number of samples/blood draws and total blood volume collected will not exceed those stated in the protocol.

Corporate Confidential Information

Corporate Confidential Information

8.4 Safety

Safety assessments are specified below; methods for assessment and recording are specified in the SOM, with the [Assessment Schedule](#) detailing when each assessment is to be performed.

8.4.1 Physical examination

A complete physical examination will include the examination of general appearance, skin, neck (including thyroid), eyes, ears, nose, throat, lungs, heart, abdomen, back, lymph nodes, and extremities, as well as avascular and neurological examination. If indicated based on medical history and/or symptoms, rectal, external genitalia, breast, and/or pelvic exams may be performed.

Information for all physical examinations must be included in the source documentation at the study site and will not be recorded in the eCRF. Significant findings that are present prior to informed consent are included in the Relevant Medical History eCRF. Significant findings observed after informed consent signature which meet the definition of an Adverse Event must be appropriately recorded on the Adverse Event eCRF.

8.4.2 Vital signs

Vital signs include body temperature, blood pressure (BP) and pulse measurements. After the patient has been sitting for 3 minutes, with back supported and both feet placed on the floor, systolic and diastolic BP will be measured using a validated device, with an appropriately sized cuff. In case the cuff sizes available are not large enough for the patient's arm circumference, a sphygmomanometer with an appropriately sized cuff may be used.

To ensure accurate measurement of heart rate or blood pressure, the Investigator may obtain a total of up to three consecutive assessments, with the patient seated quietly for approximately five minutes preceding each repeat assessment.

8.4.3 Height and weight

- Height (cm)
- Body weight (kg)
- Body mass index (BMI) will be calculated (Body weight (kg) / [Height (m)]²)

8.4.4 Laboratory evaluations

Clinically relevant deviations of laboratory test results occurring during or at completion of the study must be reported and discussed with Novartis personnel. The results should be evaluated for criteria defining an adverse event and reported as such if the criteria are met. Repeated evaluations are mandatory until normalization of the result(s) or until the change is no longer clinically relevant. In case of doubt, Novartis personnel should again be contacted.

Hematology

Hemoglobin, hematocrit, red blood cell count, white blood cell count with differential (e.g., neutrophils, basophils, eosinophils, monocytes, lymphocytes) and platelet count will be measured.

Clinical chemistry

Sodium, potassium, creatinine, urea, uric acid, chloride, albumin, total protein, calcium, alkaline phosphatase, total bilirubin, LDH, GGT, AST, ALT, amylase, lipase, CK, glucose, total cholesterol, triglycerides. If the total bilirubin concentration is above 1.5 times the upper limit of normal, direct and indirect reacting bilirubin should be differentiated.

Urinalysis

A midstream urine sample (approximately 30 mL) will be obtained, in order to avoid contamination with epithelial cells and sediments, and allow proper assessments.

A semi-quantitative “dipstick” evaluation for the following parameters will be performed: specific gravity, pH, glucose, protein, bilirubin, ketones, nitrite, leukocytes and blood.

If the dipstick result is positive for protein, nitrite, leucocytes and/or blood sample will be sent for microscopic analysis of WBC, RBC and casts.

Coagulation panel

Prothrombin time (PT) and active partial thromboplastin time (aPTT) will be assessed. Additional parameters such as International Normalized Ratio (INR) may be estimated at the discretion of the Investigator.

8.4.5 Electrocardiogram (ECG)

The Fridericia QT correction formula (QTcF) should be used for clinical decisions.

Single 12-lead ECGs are collected. The original ECGs, appropriately signed, should be collected and archived at the study site.

Each ECG tracing should be labeled with study number, patient initials, patient number, date and time, be appropriately signed and dated to confirm review, and filed in the study site source documents.

For any ECGs with patient safety concerns, two additional ECGs should be performed to confirm the safety finding. Clinically significant abnormalities should be recorded on the relevant section of the medical history/current medical conditions/AE eCRF page as appropriate.

The eCRF will contain:

- Date and time of ECG
- Heart rate
- PR interval
- RR
- QT uncorrected
- QTcF
- QRS duration

8.4.6 Pregnancy and assessments of fertility

All pre-menopausal women who are not surgically sterile will have pregnancy tests during the study. Serum pregnancy tests will be performed at screening; at all other times urine pregnancy tests may be used. Women are considered post-menopausal and not of child bearing potential if they have had 12 months of natural (spontaneous) amenorrhea with an appropriate clinical profile (e.g., age appropriate, history of vasomotor symptoms). A positive urine pregnancy test requires immediate interruption of study drug until serum β -hCG is performed and found to be negative.

8.4.7 Other safety evaluations

8.4.7.1 PPD skin test or QuantiFeron test

A purified protein derivative (PPD) skin test will be performed and read at screening in order to evaluate the infection with tuberculosis (TB). The test dose is bioequivalent to 5 tuberculin units (or as according to local standard practice) of standard PPD injected intradermally into usually the volar surface of the forearm. The site is cleansed and the PPD extract is then injected into the most superficial dermal layer of the skin. If given correctly, the injection should raise a small wheal of about 5 mm, which resolves within 10-15 minutes.

Because the reaction (induration) will take 48-72 hours to develop, the patient must return to the investigators' site within that time for a proper evaluation of the test site. This will determine whether the patients have had a significant reaction to the PPD test. A reaction is

measured in millimeters of induration (hard swelling) at the site. A PPD skin induration ≥ 5 mm is interpreted as positive result.

Based on the study site's normal practice, QuantiFeron test may replace PPD skin test at screening. A positive QuantiFeron test at screening will exclude the patients from the participation in the study.

T-SPOT or other types ELISPOT assays based on interferon-gamma release may also be used for tuberculosis diagnosis as per local practice.

Results will be available as source data and will not be recorded within the eCRF.

8.4.7.2 Infections

All occurrences of infections must be carefully monitored by the investigator. Significant findings, which meet the definition of infection, must be recorded in the Adverse Event eCRF.

8.4.8 Immunogenicity

Corporate Confidential Information

8.5 Pharmacokinetics

PK samples will be collected at the timepoints defined in the [Assessment schedule](#).

Corporate Confidential Information

Corporate Confidential Information

8.6 Other assessments

Corporate Confidential Information

Corporate Confidential Information

9 Safety monitoring

9.1 Adverse events

An adverse event (AE) is any untoward medical occurrence (i.e., any unfavorable and unintended sign [including abnormal laboratory findings], symptom or disease) in a subject or clinical investigation subject *after providing written informed consent* for participation in the study. Therefore, an AE may or may not be temporally or causally associated with the use of a medicinal (investigational) product.

The occurrence of adverse events should be sought by non-directive questioning of the patient at each visit during the study. Adverse events also may be detected when they are volunteered by the patient during or between visits or through physical examination, laboratory test, or other assessments.

Abnormal laboratory values or test results constitute adverse events only if they fulfill at least one of the following criteria:

- they induce clinical signs or symptoms,
- they are considered clinically significant,
- they require therapy.

Clinically significant abnormal laboratory values or test results should be identified through a review of values outside of normal ranges/clinically notable ranges, significant changes from baseline or the previous visit, or values which are considered to be non-typical in patients with the underlying disease(s). Investigators have the responsibility for managing the safety of individual patient and identifying adverse events. Alert ranges for liver related events are included in [Section 9.3](#).

Adverse events must be recorded on the Adverse Events CRF for patients that pass screening and enter into the study. The adverse events should be reported according to the signs, symptoms or diagnosis associated with them, and accompanied by the following information:

1. The severity grade is as follows based on CTC-AE grading:
 - 1 mild: usually transient in nature and generally not interfering with normal activities
 - 2 moderate: sufficiently discomforting to interfere with normal activities
 - 3 severe: prevents normal activities
 - 4 life threatening

CTC-AE grade 5 (death) is not used, but is collected in other CRFs (e.g. Study Completion, Death/Survival).

2. its relationship to the investigational treatment (no/yes), or other study treatment (non-investigational) (no/yes), or both or indistinguishable,
3. its duration (start and end time/dates) or if the event is ongoing, an outcome of not recovered/not resolved should be reported.
4. whether it constitutes a serious adverse event (SAE). See [Section 9.2.1](#) for the definition of SAE.
5. action taken regarding study treatment

All adverse events should be treated appropriately. Action may include one or more of the following:

- no action taken (i.e. further observation only)
- study treatment dosage adjusted/temporarily interrupted
- study treatment permanently discontinued due to this adverse event
- concomitant medication given
- non-drug therapy given
- patient hospitalized/patient's hospitalization prolonged

6. its outcome (not recovered/not resolved; recovered/resolved; recovering/resolving, recovered/resolved with sequelae; fatal; or unknown)

Once an adverse event is detected, it should be followed until its resolution or until it is judged to be permanent, and assessment should be made at each visit (or more frequently, if necessary) of any changes in severity, the suspected relationship to the study drug, the interventions required to treat it, and the outcome.

Information about common side effects already known about the investigational drug can be found in the Investigator Brochure (IB) or will be communicated between IB updates in the form of Investigator Notifications. This information will be included in the subject informed consent and should be discussed with the patient during the study as needed.

The investigator should also instruct each patient to report any new adverse event (beyond the protocol observation period) that the patient, or the patient's personal physician, believes might reasonably be related to study treatment. This information should be recorded in the investigator's source documents, however, if the AE meets the criteria of an SAE, it must be reported to Novartis in a timely manner (see [Section 9.2.2](#)).

9.2 Serious adverse event reporting

9.2.1 Definition of SAE

An SAE is defined as any adverse event (appearance of (or worsening of any pre-existing) undesirable sign(s), symptom(s) or medical conditions(s) which meets any one of the following criteria:

- is fatal or life-threatening
- results in persistent or significant disability/incapacity
- constitutes a congenital anomaly/birth defect
- requires inpatient hospitalization or prolongation of existing hospitalization, unless hospitalization is for:
 - routine treatment or monitoring of the studied indication, not associated with any deterioration in condition (Graves' disease)
 - elective or pre-planned treatment for a pre-existing condition that is unrelated to the indication under study and has not worsened since the start of study drug
 - treatment on an emergency outpatient basis for an event not fulfilling any of the definitions of a SAE given above and not resulting in hospital admission
 - social reasons and respite care in the absence of any deterioration in the patient's general condition
- is medically significant, i.e. defined as an event that jeopardizes the patient or may require medical or surgical intervention.

Life-threatening in the context of a SAE refers to a reaction in which the patient was at risk of death at the time of the reaction; it does not refer to a reaction that hypothetically might have caused death if more severe.

All malignant neoplasms will be assessed as serious under "medically significant" if other seriousness criteria are not met.

Any suspected transmission via a medicinal product of an infectious agent is also considered a serious adverse reaction.

Medical and scientific judgment should be exercised in deciding whether other situations should be considered serious reactions, such as important medical events that might not be immediately life threatening or result in death or hospitalization but might jeopardize the patient or might require intervention to prevent one of the other outcomes listed above. Examples of such events are intensive treatment in an emergency room or at home for allergic bronchospasm, blood dyscrasias or convulsions that do not result in hospitalization or development of dependency or abuse.

All AEs (serious and non-serious) are captured on the CRF, SAEs also require individual reporting to DS&E as per [Section 9.2.2](#).

9.2.2 SAE reporting

To ensure patient safety, every SAE, regardless of causality, occurring after the patient has provided informed consent and until the study completion, must be reported to Novartis within 24 hours of learning of its occurrence as described below. Any SAEs experienced after the completion of the study should only be reported to Novartis if the investigator suspects a causal relationship to study treatment.

Recurrent episodes, complications, or progression of the initial SAE must be reported as follow-up to the original episode, regardless of when the event occurs. This report must be submitted within 24 hours of the investigator receiving the follow-up information. An SAE that is considered completely unrelated to a previously reported one should be reported separately as a new event.

SAEs (initial and follow-up) that are recorded electronically in the Electronic Data Capture system should be entered, saved and e-signed within 24 hours of awareness of the SAE or changes to an existing SAE. These data will automatically be submitted to Novartis Drug Safety & Epidemiology immediately after investigator signature or 24 hours after entry, whichever occurs first. Study site personnel must also inform the Clinical Trial Leader.

Follow-up information provided should describe whether the event has resolved or continues, if and how it was treated, whether the treatment code was broken or not and whether the patient continued or withdrew from study participation. Each re-occurrence, complication, or progression of the original event should be reported as a follow-up to that event regardless of when it occurs.

If the SAE is not previously documented in the Investigator's Brochure and is thought to be related to the investigational treatment, a Drug Safety and Epidemiology Department associate may urgently require further information from the investigator for Health Authority reporting. Novartis may need to issue an Investigator Notification (IN) to inform all investigators involved in any study with the same investigational treatment that this SAE has been reported. Suspected Unexpected Serious Adverse Reactions (SUSARs) will be collected and reported to the competent authorities and relevant ethics committees in accordance with EU Guidance 2011/C 172/01 or as per national regulatory requirements in participating countries.

9.3 Liver safety monitoring

To ensure patient safety and enhance reliability in determining the hepatotoxic potential of an investigational drug, a standardized process for identification, monitoring and evaluation of liver events has to be followed.

The following two categories of abnormalities / adverse events have to be considered during the course of the study:

- Liver laboratory triggers, which will require repeated assessments of the abnormal laboratory parameter

- Liver events, which will require close observation, follow-up monitoring and completion of the standard base liver CRF pages

Please refer to [Table 9-1](#) and [Table 9-2](#) for complete definitions of liver laboratory triggers and liver events.

Every liver laboratory trigger or liver event should be followed up by the investigator or designated personal at the trial site, as summarized below and detailed in [Table 9-2](#).

For the liver laboratory trigger:

- Repeating the LFT within the next week to confirm elevation.

These LFT repeats should be performed using the central laboratory if possible. If this is not possible, then the repeats can be performed at a local laboratory to monitor the safety of the patient. Repeats laboratory should then be performed at central laboratory as soon as possible. If a liver event is subsequently reported, any local LFTs previously conducted that are associated with this event should be reported on the Liver CRF pages.

For the liver events:

- Repeating the LFT to confirm elevation as appropriate
- Discontinuation of the investigational drug (refer to [Section 7.1](#), if appropriate)
- Hospitalization of the patient if appropriate
- A causality assessment of the liver event via exclusion of alternative causes (e.g. disease, co-medications)
- An investigation of the liver event which needs to be followed until resolution.

These investigations can include serology tests, imaging and pathology assessments, hepatologist's consultancy, based on investigator's discretion. All follow-up information, and the procedures performed should be recorded as appropriate in the CRF, including the liver event overview CRF pages.

Table 9-1 Liver event and laboratory trigger definitions

	Definition/ threshold
Liver laboratory triggers	
 • $3 \times \text{ULN} < \text{ALT} / \text{AST} \leq 5 \times \text{ULN}$ • $1.5 \times \text{ULN} < \text{TBL} \leq 2 \times \text{ULN}$
Liver events	
 • $\text{ALT or AST} > 5 \times \text{ULN}$ • $\text{ALP} > 2 \times \text{ULN}$ (in the absence of known bone pathology) • $\text{TBL} > 2 \times \text{ULN}$ (in the absence of known Gilbert syndrome) • $\text{ALT or AST} > 3 \times \text{ULN}$ and $\text{INR} > 1.5$ • Potential Hy's Law cases (defined as $\text{ALT or AST} > 3 \times \text{ULN}$ and $\text{TBL} > 2 \times \text{ULN}$ [mainly conjugated fraction] without notable increase in ALP to $> 2 \times \text{ULN}$) • Any clinical event of jaundice (or equivalent term) • $\text{ALT or AST} > 3 \times \text{ULN}$ accompanied by (general) malaise, fatigue, abdominal pain, nausea, or vomiting, or rash with eosinophilia • Any adverse event potentially indicative of a liver toxicity *

Table 9-2 Follow up requirements for liver events and laboratory triggers

Criteria	Actions required	Follow-up monitoring
Potential Hy's Law case ^a	
 • Discontinue the study drug immediately • Hospitalize, if clinically appropriate • Establish causality • Complete liver CRF 	ALT, AST, TBL, Alb, PT/INR, ALP and γGT until resolution ^c (frequency at investigator discretion)
ALT or AST		
> 8 × ULN	
 • Discontinue the study drug immediately • Hospitalize if clinically appropriate • Establish causality • Complete liver CRF 	ALT, AST, TBL, Alb, PT/INR, ALP and γGT until resolution ^c (frequency at investigator discretion)
> 3 × ULN and INR > 1.5	
 • Discontinue the study drug immediately • Hospitalize, if clinically appropriate • Establish causality • Complete liver CRF 	ALT, AST, TBL, Alb, PT/INR, ALP and γGT until resolution ^c (frequency at investigator discretion)
> 5 to ≤ 8 × ULN	
 • Repeat LFT within 48 hours • If elevation persists, continue follow-up monitoring • If elevation persists for more than 2 weeks, discontinue the study drug • Establish causality • Complete liver CRF 	ALT, AST, TBL, Alb, PT/INR, ALP and γGT until resolution ^c (frequency at investigator discretion)
> 3 × ULN accompanied by symptoms ^b	
 • Discontinue the study drug immediately • Hospitalize if clinically appropriate • Establish causality • Complete liver CRF 	ALT, AST, TBL, Alb, PT/INR, ALP and γGT until resolution ^c (frequency at investigator discretion)
> 3 to ≤ 5 × ULN (patient is asymptomatic)	
 • Repeat LFT within the next week • If elevation is confirmed, initiate close observation of the patient 	
Investigator discretion
 
Monitor LFT within 1 to 4 weeks

ALP (isolated)		
> 2 × ULN (in the absence of known bone pathology)	
 • Repeat LFT within 48 hours • If elevation persists, establish causality • Complete liver CRF 	
Investigator discretion
 
Monitor LFT within 1 to 4 weeks or at next visit

Criteria	Actions required	Follow-up monitoring
TBL (isolated)		
> 2 × ULN (in the absence of known Gilbert syndrome)	
 Repeat LFT within 48 hours If elevation persists, discontinue the study drug immediately Hospitalize if clinically appropriate Establish causality Complete liver CRF 	ALT, AST, TBL, Alb, PT/INR, ALP and γGT until resolution ^c (frequency at investigator discretion) Test for hemolysis (e.g. reticulocytes, haptoglobin, unconjugated [indirect] bilirubin)
> 1.5 to ≤ 2 × ULN (patient is asymptomatic)	
 Repeat LFT within the next week If elevation is confirmed, initiate close observation of the patient 	Investigator discretion Monitor LFT within 1 to 4 weeks or at next visit
Jaundice	
 Discontinue the study drug immediately Hospitalize the patient Establish causality Complete liver CRF 	ALT, AST, TBL, Alb, PT/INR, ALP and γGT until resolution ^c (frequency at investigator discretion)
Any AE potentially indicative of a liver toxicity*	
 Consider study drug interruption or discontinuation Hospitalization if clinically appropriate Establish causality Complete liver CRF 	Investigator discretion

*These events cover the following: hepatic failure, fibrosis and cirrhosis, and other liver damage-related conditions; the non-infectious hepatitis; the benign, malignant and unspecified liver neoplasms

^aElevated ALT/AST > 3 × ULN and TBL > 2 × ULN but without notable increase in ALP to > 2 × ULN

^b(General) malaise, fatigue, abdominal pain, nausea, or vomiting, or rash with eosinophilia

^cResolution is defined as an outcome of one of the following: (1) return to baseline values, (2) stable values at three subsequent monitoring visits at least 2 weeks apart, (3) remain at elevated level after a maximum of 6 months, (4) liver transplantation, and (5) death.

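### Read literally, Table 9-2 mandates weaker action for TBL > 2 × ULN when ALP and ALT/AST are also raised than when bilirubin is raised alone

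*Protocol*

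**What the plan says.** Table 9-1 of the protocol makes TBL > 2 × ULN a liver event, with one exception: it counts only "in the absence of known Gilbert syndrome". Neither ALP nor ALT/AST enters that definition. Section 9.3 says that liver events are followed up as detailed in Table 9-2.

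The laboratory rows of Table 9-2 that matter here are:

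- **Potential Hy's Law case:** stop immediately. Footnote a defines it as ALT/AST > 3 × ULN and "TBL > 2 × ULN but without notable increase in ALP to > 2 × ULN".
- **Isolated TBL > 2 × ULN:** repeat within 48 hours, then "If elevation persists, discontinue the study drug immediately".
- **ALT/AST > 5 to ≤ 8 × ULN:** repeat within 48 hours, then "If elevation persists, continue follow-up monitoring". A stop is required only if the elevation lasts more than two weeks.
- **ALT/AST > 3 to ≤ 5 × ULN, asymptomatic:** repeat within a week, then "If elevation is confirmed, initiate close observation of the patient". The follow-up column adds "Monitor LFT within 1 to 4 weeks". There is no stop.
- **Isolated ALP > 2 × ULN:** repeat within 48 hours and establish causality. There is no stop.

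ALT/AST > 8 × ULN, ALT/AST > 3 × ULN with INR > 1.5 or with symptoms, and jaundice each force an immediate stop whatever the ALP.

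**The concern.** A stopping table should not become more lenient as more liver tests become abnormal. Here it appears to. At a fixed bilirubin above 2 × ULN, a new rise in ALP removes the Hy's Law stop through footnote a. The accompanying rise in ALT/AST then takes the patient out of the isolated TBL row. The remaining action is keyed to the transaminase level and takes no account of bilirubin. No rationale for this is given.

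What is at stake is whether an immunomodulatory antibody may be re-dosed while bilirubin stays above twice normal. The decision would rest on case-by-case judgement in a section whose stated aim is a standardised process.

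**Working it through.** The plan gives no figure to reproduce; this is a check of decision rules.

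**Step 1. Apply the rows.** Fix TBL > 2 × ULN, no known Gilbert syndrome, no symptoms, INR ≤ 1.5 and no jaundice. Cross four ALT/AST bands with two ALP bands (4 × 2 = 8 patterns) and keep the strongest matching laboratory row. The benchmark is the isolated TBL action: repeat within 48 hours, stop if persistent. Because *isolated* is undefined, take two readings: (A) neither ALT/AST nor ALP is raised; (B) ALT/AST is not raised.

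| ALT/AST (× ULN) | ALP ≤ 2 × ULN (A and B) | New ALP > 2 × ULN, reading A | New ALP > 2 × ULN, reading B |
|---|---|---|---|
| ≤ 3 | TBL row: benchmark | no laboratory row fits: weaker | TBL row: benchmark |
| > 3 to ≤ 5 | Hy's Law: stop now | repeat within a week, observe: weaker | same: weaker |
| > 5 to ≤ 8 | Hy's Law: stop now | stop only after > 2 weeks: weaker | same: weaker |
| > 8 | stop now | stop now | stop now |

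Weaker than the benchmark: 3 of 8 patterns under A, 2 of 8 under B, all with ALP > 2 × ULN. With ALP ≤ 2 × ULN the count is 0 of 4 under both. The two bands from > 3 to ≤ 8 × ULN are weaker under either reading. The ≤ 3 × ULN band depends on which is meant.

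**Step 2. Follow a Day 29 sample.** Infusions are on Days 1, 15, 29, 57 and 85 (Section 3.1).

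- *TBL 3 × ULN alone:* repeat by Day 29 + 2 = 31; stop if persistent; 0 further infusions.
- *TBL 3 ×, ALP 3 ×, ALT 4 × ULN:* repeat by Day 29 + 7 = 36. The 1-to-4-week liver test falls on Days 36 to 57 counted from Day 29 (29 + 7, 29 + 28), or Days 43 to 64 counted from a Day 36 confirmation (36 + 7, 36 + 28). It may therefore come as late as 64 − 57 = 7 days after the Day 57 infusion. No result mandates a stop while the pattern is unchanged. Days 57 and 85 stay permitted: 2 of 5 infusions, or 2 × 10 = 20 of 5 × 10 = 50 mg/kg.
- *TBL 3 ×, ALP 3 ×, ALT 6 × ULN:* if ALT stays up, the stop applies after Day 29 + 14 = 43, before Day 57. There are 0 extra infusions unless ALT falls to ≤ 5 × ULN while TBL stays up.

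Table 8-1 marks chemistry on Days 29 and 85 but not on Day 57. Its chemistry footnote is redacted, so nothing above relies on a missing Day 57 sample.

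**Step 3. Look for a mandated stop elsewhere.** Section 7.1 obliges the investigator to stop on believing that continuation is detrimental; it has no liver threshold. Section 9.3 lists discontinuation for liver events where appropriate. The Table 9-2 row for adverse events suggesting liver toxicity says "Consider study drug interruption or discontinuation". Section 6.3 leaves interruption to the investigator's discretion. Section 8.4.4 mandates repeat testing and discussion with the sponsor, and Section 9.6 provides for joint safety review. None of these requires a stop on a bilirubin value.

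**The case against.** The strongest reply is that *isolated* only separates the TBL row from the combined Hy's Law row. Every liver event in Table 9-1 is meant to be handled through Table 9-2, and the TBL row is the only one there for TBL > 2 × ULN outside Hy's Law. On that reading the row covers every such case and the gap is 0 of 8 patterns. This is possible, and it is why the point is confined to the literal reading. But it requires *isolated* to mean *not Hy's Law*, which the table does not say; two other raised liver parameters do not fit the ordinary meaning of the word.

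A second reply is that ALT/AST > 3 to ≤ 5 × ULN is only a laboratory trigger, so its row should not govern a liver event. It is true that the event brings causality assessment, liver CRF pages and "An investigation of the liver event which needs to be followed until resolution". Those duties secure testing and review; they do not supply the stop.

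A third is that 2 of 5 infusions overstates the exposure. That stands in part. It is an upper bound: the pattern must persist without symptoms or jaundice, and the investigator and sponsor must choose to continue after mandatory discussion. The pattern counts are table cells, not patients.

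A reader might also infer that the protocol has no means of stopping such a patient, or that dosing would continue. The documents do not support either: discretionary routes to a stop exist in several sections, and an event judged medically significant would also be reported as an SAE within 24 hours.

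**Conclusion.** The point holds as an inconsistency in the mandated action under a literal reading of Table 9-2. TBL > 2 × ULN with a new ALP > 2 × ULN and ALT/AST > 3 to ≤ 8 × ULN, without symptoms, INR > 1.5 or jaundice, is handled less strictly than TBL > 2 × ULN alone.

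The consequence lies mainly in the > 3 to ≤ 5 × ULN band, with at most two further infusions after a Day 29 finding. In the > 5 to ≤ 8 × ULN band the difference is normally one of timing, without an extra dose.

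The conclusion assumes the ordinary meaning of *isolated* and a new ALP rise. Exclusion 16 admits ALP up to 5 × ULN, and footnote a does not say how a pre-existing elevation counts. The wider claim, that raised TBL and ALP with ALT/AST ≤ 3 × ULN also lacks a stop, holds only under reading A and is not asserted. The documents give no frequency for the pattern, and none is estimated. The correction is worth making because it is cheap and removes an illogical safety rule.

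**What to change.** State in Table 9-2 that the TBL > 2 × ULN row (repeat within 48 hours, stop if persistent, known Gilbert syndrome excepted) is the minimum action whether or not ALT/AST or ALP is raised. Add that when several rows match, the strongest governs. Both parts are needed: removing the word *isolated* alone would leave true Hy's Law cases matching two rows of different urgency, and those cases must still stop immediately.

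The cost is one short change to the table in a protocol amendment, with no extra scheduled visits. The downside is an occasional earlier stop in a patient with a cholestatic pattern, which the protocol already requires for the same bilirubin on its own.
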